1. INTRODUCTION

1.1. Background on the Disease

Worldwide, the overall lifetime prevalence of schizophrenia is around 1% of the general population and the majority of patients with schizophrenia have moderate to severe negative symptoms at different times during their life (Simeone 2015; Error! Reference source not found. 2010).

Negative symptoms are an integral feature of schizophrenia and often emerge during the prodromal phase, before the full-blown manifestation of positive (psychotic) symptoms that lead to the diagnosis of schizophrenia (Piskulic 2012; Yung 2019; Sauvé 2019; Carpenter WT Jr, Buchanan RW. Negative symptom therapeutics. Schizophr Bull. 2017;43:681-682.

Devoe 2021). Negative symptoms thus constitute a major burden on patients, their families, and society (Foussias 2014; Strauss 2010; Galderisi 2018).

Negative symptoms include emotional experiences such as avolition, asociality, and anhedonia as well as abnormal expression such as blunted affect and poverty of speech (Giordano GM, Caporusso E, Pezzella P, et al. Updated perspectives on the clinical significance of negative symptoms in patients with schizophrenia. Exp Review Neurother. 2022.

Kirkpatrick B. Developing concepts in negative symptoms: primary vs secondary and apathy vs expression. J Clin Psychiatry. 2014;75:3-7.

Kirkpatrick 2017). Avolition or the lack of will to start and continue pleasurable or essential daily activities is a central feature of primary negative symptoms (Error! Reference source not found. 2020; Trémeau 2012; Kirschner M, Aleman A, Kaiser S. Secondary negative symptoms-a review of mechanisms, assessment and treatment. Schizophr Res. 2017;186:29-38.

Messinger 2011) and reducing its severity probably drives the overall improvements in negative symptoms (Strauss 2020; Strauss 2021). Simply put, negative symptoms encompass a reduction or absence of the normal range of emotions and behaviors.

Negative symptoms are categorized by researchers and clinicians into primary negative symptoms, that are intrinsic to the schizophrenic illness, and secondary negative symptoms, that manifest as the adverse effect of antipsychotic drugs or can be the result of avoiding social interactions in response to threatening delusions and hallucinations (Artaloytia 2006; Kirschner 2017; Carpenter 2017; Giordano GM, Caporusso E, Pezzella P, et al. Updated perspectives on the clinical significance of negative symptoms in patients with schizophrenia. Exp Review Neurother. 2022.

Kirkpatrick 2014). The current instruments used to measure the severity and therapeutic induced changes in negative symptoms comprise Positive and Negative Symptom Score- (PANSS-)

derived constructs (White 1997; Marder 1997), other scales focused exclusively on negative symptoms such as the Brief Negative Symptoms Scale (BNSS) (Giordano GM, Caporusso E, Pezzella P, et al. Updated perspectives on the clinical significance of negative symptoms in patients with schizophrenia. Exp Review Neurother. 2022.

Kirkpatrick 2011) and NSA-16 (Axelrod 1993), and remote digital measurements (Cohen 2021). However, opinions about which instrument is best to measure changes in these manifestations continue to evolve (Error! Not a valid bookmark self-reference. 2022; Giordano 2022).

Unfortunately, there are no approved treatments for negative symptoms of schizophrenia in the United States (US). Therefore, the treatment of primary negative symptoms of schizophrenia and the resulting functional deficits remains a serious unmet need and meets the criteria for a serious or life-threatening disease or condition.

1.2. Background on the Study Drugs

Roluperidone is a novel cyclic amido derivative, with affinity and antagonistic activity at the 5-hydroxytryptamine-2A (5-HT_{2A}), sigma₂, α_{1A} -adrenergic, and, to a lesser extent, α_{1B} -adrenergic receptors. Its metabolite, BFB-520, has a comparable profile to roluperidone, with lower affinity for sigma₂ receptors, and lower affinity for 5-HT_{2A} receptors. Roluperidone has very low or no affinity to, or antagonistic activities on, dopaminergic, muscarinic, cholinergic, and histaminergic receptors. Hence, roluperidone mainly targets 5-HT_{2A}, sigma₂, α_{1A} - and α_{1B} -adrenergic pathways without direct blockade of dopaminergic pathways/receptors and, in particular, the D₂ dopaminergic receptor sub-type, which is the main target of most available antipsychotics to alleviate psychotic symptoms of patients afflicted by schizophrenia.

Because roluperidone lacks antagonistic activity at the D_2 receptors, it exerts its pharmacologic effect without blocking the brain's dopamine- (DA-) driven reward systems. Therefore, roluperidone does not induce secondary negative symptoms such as sedation and Parkinsonism. Unlike most antipsychotics, it does not, at therapeutic doses, increase prolactin levels or cause weight gain or akathisia.

Nevertheless, it is possible that roluperidone modulates both dopaminergic and glutamatergic pathways without blocking DA receptors, in addition to its effects on neuroplasticity and brain cholesterol metabolism (data on file). The various effects of roluperidone in the different brain areas can be explained by the complexity of the mesolimbic and mesocortical pathways and their role in schizophrenia. Moreover, the antagonist properties of roluperidone on its main targets (5-HT_{2A}, sigma₂, α_{1A} -adrenergic, and α_{1B} -adrenergic receptors) can contribute to the regulation of the imbalance between DA, glutamate, and serotonin. Indeed, these targets are involved in the modulation of the different pathways involved in positive and negative symptoms of schizophrenia.

Roluperidone is intended for the treatment of negative symptoms of schizophrenia. Roluperidone should be used as monotherapy, ie, non-adjunctively with antipsychotics. Due to a risk of QT prolongation that is known to be partly related to the CYP2D6 metabolism of metabolite BFB-520, roluperidone is only intended for patients who have at least 1 CYP2D6 allele with normal function.

Additional information about roluperidone is provided in the Investigator's Brochure.

Olanzapine is among the most frequently used drugs to treat acute exacerbation of psychosis in schizophrenia. Once psychosis ameliorates or stabilizes, olanzapine is used as maintenance

treatment to reduce the risk of recurrence of psychosis. Olanzapine has affinities for dopaminergic, cholinergic, serotonergic, and histaminergic receptors. As such it can produce extrapyramidal, parkinsonian effects, sedation, constipation, blurry vision, and weight gain.

1.3. Overall Rationale for the Study

The efficacy of roluperidone monotherapy in the treatment of negative symptoms of schizophrenia has been established in two adequate and well-controlled multinational clinical trials (MIN-101C03 and MIN-101C07). These effects have been demonstrated across both psychometric (PANSS, Negative Symptom Factor Score, BNSS, etc.) and global and functional outcomes (CGI-S and Personal and Social Performance, respectively). Since there exists the possibility that roluperidone might be prescribed off-label in concomitance with antipsychotics, the rationale of this clinical trial is to evaluate the pharmacodynamic and pharmacokinetic effects of the concomitant therapy of roluperidone with an established and widely used antipsychotic, such as olanzapine in order to provide further guidance to clinical practitioners that may prescribe off-label these drugs concomitantly in clinical practice.

2. OBJECTIVES AND ENDPOINTS

Objectives	Endpoints						
To evaluate the pharmacodynamics (PD), including safety and tolerability of the coadministration of roluperidone 64 mg and olanzapine	Safety assessments, including adverse events (AEs), clinical laboratory, electrocardiogram (ECG), vital signs, extrapyramidal symptoms (assessed by Abnormal Involuntary Movement Scale [AIMS] and Barnes Akathisia Rating Scale [BARS]), and suicidal ideation (assessed by the Columbia Suicide Severity Rating Scale [C-SSRS])						
To evaluate the effect of the coadministration of roluperidone and olanzapine on the pharmacokinetics (PK) of roluperidone in subjects with moderate to severe negative symptoms of schizophrenia	 The plasma pharmacokinetic parameters of roluperidone and its metabolite, BFB-520, following single dose and at steady state (C_{max}, T_{max}, AUC₀₋₂₄, AUC_∞) Plasma pharmacokinetic parameters of roluperidone and BFB-520 when administered concomitantly with olanzapine The plasma pharmacokinetic parameters of olanzapine administered concomitantly with roluperidone compared to its pharmacokinetic profile based on monotherapy administration from published literature 						
	Clinical Global Impression- Severity Rating (CGI-S)						

3. OVERVIEW OF STUDY DESIGN

3.1. Study Design

This is a prospective, open-label, one-sequence, inpatient, clinical study of CYP2D6 normal metabolizer (NM) subjects with moderate to severe negative symptoms of schizophrenia. be coadministered to subjects already being administered roluperidone to determine its effect on the PD and PK of roluperidone. Eligible subjects will undergo 3 study phases as follows:

- Screening Phase: Between 2 and up to 28 days during which study eligibility will be established and subjects receiving psychotropics will be washed out. Discontinuation of psychotropics must occur at least 2 days prior to the start of Treatment Period 1 (Day 1). Subjects will be admitted to the site on Day -2 and complete a Baseline Visit on Day -1.
- **Treatment Phase 1**: After the Baseline Visit (Day -1), roluperidone 64 mg/day will be administered as a monotherapy for 7 days (Days 1-7).
- Treatment Phase 2: Concomitant administration of olanzapine 10 mg/day and roluperidone 64 mg/day for 10 days, starting on Day 8 (Days 8-17). Subjects may be discharged from the clinic at least 48 hours after the last administration of the study drugs and after the collection of the last plasma sample; however, the inpatient period may be extended at the discretion of the investigator.

An End of Study (EOS) visit will take place at least 14 days after the last dose of study treatment. After the EOS visit, the medications and clinical care of the subject will be managed

Figure 1: Study Design Diagram

as per the judgement of the investigator/clinician.

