- 2. Male or female subject, 18 to 55 years of age, inclusive, and body mass index (BMI) < 35 kg/m² at Screening.
- 3. Subject meets the diagnostic criteria for schizophrenia as defined in the Diagnostic and Statistical Manual of Mental Disorders-Fifth Edition (DSM-5), as established by a full psychiatric interview in conjunction with the Mini International Neuropsychiatric Interview (MINI)¹.
- 4. Has a caregiver or family member or health care personnel who can provide information towards assessment and support the subject in terms of compliance with the protocol.
- 5. Has documented diagnosis of schizophrenia for at least 1 year before screening into the trial.
- 6. Subject is stable in terms of both positive and negative symptoms of schizophrenia over the last 3 months according to his or her clinician and/or a caregiver who knows the patient like the responsible person at the patient residence, a social worker, rehabilitation therapist or a caregiver/ family member or based on documentation in the clinical chart or medical records. Subjects with or without positive symptoms are allowed if these symptoms are stable for the last 3 months and they do not meet exclusion criterion 2.
- 7. Subject is currently an outpatient and has not been hospitalized for the last 3 months for acute exacerbation or symptoms worsening. Subjects who have been hospitalized for

_

¹ Current version for DSM-5.

- social reasons for any time period during the last 3 months or are currently hospitalized for social reasons can be included only with Sponsor's Responsible Medical Officer's approval. The social reasons must be documented in the case report form (CRF).
- 8. Subject with a score of > 20 on the PANSS original negative symptoms subscale score (sum of N1+N2+N3+N4+N5+N6+N7) at Screening and Baseline (Day -1) AND < 4 points absolute difference between the 2 visits.
- 9. Subject has discontinued psychotropic medications without risk to their clinical status or safety by Baseline (Day -1). Subjects receiving treatment with long-acting or depot antipsychotic medication must have discontinued the depot antipsychotic for a full cycle of the drug (ie, 1-6 months depending on formulation).
- 10. No history of violence against self or others during the last 1 year.

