- 9. Subject has discontinued psychotropic medications without risk to their clinical status or safety by Baseline. Subjects receiving treatment with long-acting or depot antipsychotic medication must have discontinued the depot antipsychotic for a full cycle of the drug (ie, 1-6 months depending on formulation).
- 10. No history of violence against self or others during the last 1 year.
- 11. Female subject, if not of childbearing potential, must be a woman who is post-menopausal (defined as spontaneous amenorrhoea for at least 1 year or spontaneous amenorrhoea for at least 6 months confirmed by follicle stimulating hormone result of \geq 40 IU/mL) or permanently sterilized (eg, tubal occlusion, hysterectomy, bilateral salpingectomy).
- 12. Female subject, if of childbearing potential, must test negative for pregnancy and must be using a 2 methods of contraception for at least 30 days after the completion of the study, one of which must be a highly effective method. The following highly effective contraception methods acceptable for this study are:
 - Surgical sterilization (for example, bilateral tubal ligation/salpingectomy, hysterectomy for female subjects or vasectomy for her male partner provided that the partner is the sole sexual partner of the female subject and that the vasectomized partner has received medical assessment of the surgical success).
 - Placement of an intrauterine device (IUD) or intrauterine system (IUS).
 - Hormonal contraception (oral, implantable, patch, injectable).
 - True sexual abstinence when this is in line with the preferred and usual lifestyle of the subject. Periodic abstinence (for example, calendar ovulation, sympto-thermal, post-ovulation methods), declaration of abstinence for the duration of the study, and withdrawal are NOT acceptable methods of contraception).

The following acceptable methods can be used as a second form of contraception during the study:

- Barrier methods for a female subject include use of an occlusive cap (diaphragm or cervical/vault caps) with spermicidal foam, gel, film, cream, or suppository.
- A male subject who has been sterilized (with medical assessment of the surgical success) or have partners of non-childbearing potential (including homosexual men) is

required to use a condom with spermicide. This is to prevent unintended exposure of the partner to the study drug via seminal fluid.

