- 16. Subject with clinically significant abnormalities in hematology, blood chemistry, ECG, or physical examination not resolved by the Baseline visit which according to Investigator can interfere with study participation.
- 17. Current systemic infection (eg, Hepatitis B, Hepatitis C, human immunodeficiency virus [HIV], tuberculosis). Subjects with positive Hepatitis B core antibody test and negative Hepatitis B Surface Antigen (HBsAg) may be included in the study if aminotransferase levels (alanine aminotransferase [ALT] and aspartate aminotransferase [AST]) do not exceed 2 times upper limit of normal (ULN).
- 18. Positive for COVID-19 virus.
- 19. Subject who requires or may require concomitant treatment with any other medication likely to increase QT interval (eg, paroxetine, fluoxetine, duloxetine, amiodarone; a non-exhaustive list is provided in ATTACHMENT 1: Prohibited Concomitant Medications).
- 20. Subject who requires medication inhibiting CYP2D6.
- 21. Subject with a clinically significant ECG abnormality that could be a safety risk in the study, including QT interval value corrected for heart rate using the Fridericia's formula (QTcF) > 430 msec for males and > 450 msec for females.
- 22. Subject with a myocardial infarction within 6 months of Screening based on medical history or significant ECG findings at Screening.
- 23. Familial or personal history of long QT syndrome or with additional risk factors for Torsade de Pointes.
- 24. Subject whose safety laboratory results show one or more of the following: potassium <3.4 mmol/L, or calcium <2.07 mmol/L, or magnesium <0.70 mmol/L.
- 25. Subjects with unexplained syncope.
- 26. Woman of child-bearing potential, or man, who is unwilling or unable to use accepted methods of birth control.

77 Woman with a positive pregnancy test, who is lactating or who is planning to become

- 27. Woman with a positive pregnancy test, who is lactating, or who is planning to become pregnant during the study.
- 28. Subject who participated in another clinical study within 3 months prior to Screening, or received roluperidone previously, or has previously participated in > 3 clinical studies with experimental medication within the past 2 years.

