6.1.1. Screening Phase

During the screening phase subjects and their legal representatives must provide written informed consent before any study evaluations are performed or any laboratory samples are collected. After written informed consent is obtained, subjects will be evaluated for study eligibility during the screening period. A complete medical history will be documented, and a complete physical examination will be conducted, including measurement of vital signs, electrocardiogram (triplicate ECG), body weight, and height. Hematology, clinical chemistry, serology, and urinalysis will be performed for all subjects, as well as verification of CYP2D6 genotype (confirmed by study-specific testing). AIMS, CGI-S, BARS, and C-SSRS will also be administered. All psychotropic drugs must be discontinued by Day -2; the time and rate of psychotropic discontinuation will be at the discretion of the investigator.

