Itraconazole	Imipramine	Phospho-diesterase 3	Tacrolimus			
Ketoconazole	Fluoxetine	inhibitor:	Tamoxifen			
Pentamidine	Fluvoxamine	Anagrelide	Terlipressin			
Posaconazole	Mirtazapine	cilostazol	Terolidine			
Voriconazole	Nortriptyline		Tetrabenazine			
Antiviral	Paroxetine		Tiapride			
atazanavir	Sertraline		Tizanidine			
Efavirenz	Trazodone		Tolterodine			
Nelfinavir	Trimipramine		Toremifene			
Ritonavir	Venlafaxine		Vandetanib			
Saquinavir			Vardenafil			
Telaprevir			Vemurafenib			
Voriconazole			Vorinostat			
Underlined: known risk of TdP;						
Highlighted grey: possible risk of TdP;						
Otherwise: conditional risk of TdP: eg, in case of overdose, DDI or electrolytes imbalance.						
·						

[figure not shown]
CYP2D6 Inhibitors				
Anti-infectives	Others			
Chloroquine	Bupropion			
Quinacrine	Celecoxib			
	Cinacalcet			
Cardiovascular	Chlorpheniramine			
Amiodarone	Cimetidine			
Aprindine	Clemastine			
Mibefradil	cocaine			
Propafenone	Codeine			
Labetalol	Delavirdine			
Quinidine	Dextropropoxyphene			
	Diltiazem			
Antidepressants	Diphenhydramine			
Amitriptyline	Doxorubicin			
Citalopram	Entacapone (high doses)			
Clomipramine	Halofantrine			
Doxepin	Hydroxyzine			
Duloxetine	Indinavir			
Escitalopram	Imatinib			
Fluoxetine	Lobelin			
Fluvoxamine	Lomustine			
Paroxetine	Methadone			
Sertraline	Moclobemide			
	Metoclopramide			
Antipsychotics	Midodrine			
Chlorpromazine	Moclobemide			
Fluphenazine	Nortuloxeline			
Haloperidol	Ranitidine			
Levomepromazine	Ritonavir			
Perphenazine	Ticlopidine			
Promethazine	Tripelennamine			
Risperidone (weak)	Vinblastine			
Sertindole	Vincristine			
Thioridazine	Vinorelbine			
	Yohimbine			

[figure not shown]

[figure not shown]
 1	, ,				1	
	■				▮ ■	
	▮	-		 		
-	-	•	-	•	-	-
 		ı	_			_
 			 			

[figure not shown]

[figure not shown]

[figure not shown]

[figure not shown]

[figure not shown]

[figure not shown]

[figure not shown]

[figure not shown]

[figure not shown]

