4.4. PK COMPLETER SET

The PK Completer set will consist of all subjects who completed all the PK assessments, up to and including the 48-hour PK blood sample collection, provided they have no major protocol violations that could affect the pharmacokinetics of roluperidone. Select PK evaluations (C_{max} , AUC_{24} , AUC_{last} , and AUC_{∞}) will be performed for the PK Completer set.

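### A recently stopped, slowly eliminated CYP2D6 inhibitor or a depot antipsychotic can still act on Day 7, lowering the BFB-520 combination/alone ratio; no analysis is planned to show it

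*Protocol*

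**What the plan says.** **Stopping oral psychotropics.** Protocol 3.1 (repeated in the Synopsis and SAP 1.1): "Discontinuation of psychotropics must occur at least 2 days prior to the start of Treatment Period 1 (Day 1". Protocol 6.1.1: "All psychotropic drugs must be discontinued by Day -2", with time and rate of withdrawal left to the investigator. Inclusion criterion 9 in the Synopsis: "Subject has discontinued psychotropic medications without risk to their clinical status or safety by Baseline (Day -1"; Section 4.2 has the same criterion without the day number.

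**Depots.** Under the same criterion, subjects "must have discontinued the depot antipsychotic for a full cycle of the drug (ie, 1-6 months depending on formulation". The point from which the cycle is counted is not given.

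**CYP2D6.** Exclusion 20 reads "Subject who requires medication inhibiting CYP2D6". It has no look-back period. Attachment 1 lists CYP2D6 inhibitors, among them fluoxetine, paroxetine, duloxetine, sertraline, haloperidol, fluphenazine, perphenazine and (as weak) risperidone. Inclusion 13 establishes metaboliser status by genotype. Protocol 1.2 restricts the intended population: "Due to a risk of QT prolongation that is known to be partly related to the CYP2D6 metabolism of metabolite BFB-520".

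**Analysis.** SAP 4.3 and 4.4 keep subjects with the required PK assessments, "provided they have no major protocol violations that could affect the pharmacokinetics of roluperidone". SAP 5.2.4 forms steady-state ratios of combination to roluperidone alone and fits a mixed model with treatment as the fixed term and subject as the random term. Full profiles are taken on Days 1, 7 and 17 (SAP 5.2.1). SAP 5.3.3 only lists prior medications.

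**The concern.** The Day 17/Day 7 ratio measures an olanzapine effect only if nothing else that changes the clearance of the analyte differs between those days. The subjects are people with schizophrenia coming off psychotropics, several of which the protocol itself names as CYP2D6 inhibitors. Genotyping cannot detect inhibition by a drug that is still being cleared. A subject who has stopped such a drug does not *require* it, so exclusion 20 does not apply, and having followed the rules is not a protocol violation, so the SAP PK sets do not remove the subject.

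Residual inhibitor is always higher on Day 7 than on Day 17. If CYP2D6 clears BFB-520, which is the natural reading of Protocol 1.2, BFB-520 exposure would then fall between the two days whatever olanzapine does. With one sequence and no period term, the model assigns that fall to treatment. The error is in the reassuring direction: it hides an increase in the metabolite linked to QT risk, in a study that Protocol 1.3 says should guide prescribers.

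**Working it through.** **1. The plan's own figure.** Protocol 8.1 gives maximum imprecision of 20.5% and 30.8% for within-subject SD 0.25 and 0.40. With 12 completers, a 90% interval and 90% assurance on the sample SD:

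h = t(0.95; 11) × SD × √(2/12) × √(χ²(0.90; 11)/11), and imprecision = 1 − exp(−h)

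- SD 0.25: h = 1.796 × 0.25 × 0.408 × 1.253 = 0.230, giving 20.5%.
- SD 0.40: h = 0.368, giving 30.8%.

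Both reproduce. They describe random error only; carry-over is a bias and lies outside them.

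**2. Elapsed time.** There is no Day 0. A last dose on Day -2 is 2 days before Day 1, 8 days before Day 7 and 18 days before Day 17. A last dose on Day -1 gives 7 and 17 days.

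**3. Effect on the ratio in one affected subject, true olanzapine effect = 1.** The documents give no inhibitor half-life T, no inhibition strength and no CYP2D6 share of clearance (fm), so all three are assumed. For a reversible inhibitor:

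- fraction left f = 2^(−days/T)
- relative exposure E = 1/[(1 − fm) + fm/(1 + I × f)]
- ratio = E(Day 17)/E(Day 7)

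Worked example with fm = 0.8, I = 10, T = 5 days, stopped Day -2:

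- f is 0.330 on Day 7 and 0.082 on Day 17.
- E is 2.59 on Day 7 and 1.57 on Day 17.
- The ratio is 1.57/2.59 = 0.60.

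Set A: fm 0.5-0.8, I 3-10 (clearance by that route cut 4- to 11-fold). Set B: fm 0.3-0.9, I 1-4. Both stopped on Day -2.

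| T (days) | Set A | Set B |
|---|---|---|
| 1 | 0.97-0.99 | 0.99-1.00 |
| 2 | 0.70-0.92 | – |
| 3 | – | 0.69-0.96 |
| 5 | 0.60-0.83 | – |
| 7 | – | 0.66-0.95 |
| 10 | 0.78-0.91 | – |
| 14 | – | 0.78-0.96 |
| 21 | 0.88-0.97 | 0.84-0.97 |

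The bias is small for short half-lives, because little is left by Day 7, and shrinks again for very long ones, because little changes in ten days.

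**4. Depots.** Suppose set B inhibition (I of 1-4) is still present on Day 1, 6 days before Day 7 and 16 before Day 17. The ratio is then 0.84-0.98 for T = 21 days and 0.94-0.99 for T = 60 days.

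**5. Effect on the geometric mean ratio.** If a proportion p of subjects has ratio R, the mean ratio is multiplied by R^p. R = 0.80 gives 0.80^0.25 = 0.95 with a quarter affected and 0.80^0.5 = 0.89 with half. Three of 12 at R = 0.70 gives 0.70^0.25 = 0.91. For scale, exp(±t × SD × √(2/12)) around a true ratio of 1 gives an expected 90% interval of 0.83-1.20 (SD 0.25) or 0.75-1.34 (SD 0.40).

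**6. Cost of leaving subjects out.** The step 1 formula with 9 subjects gives 24.7% and 36.4%; with 6 it gives 32.7% and 46.9%.

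**The case against.** - **The gap is eight days, not one or two.** A reader might infer from the stopping rule that any subject who stopped just before dosing contaminates the reference. The table does not support this: with a 1-day half-life the bias is about 3% at most. Only slowly eliminated inhibitors and some depots matter.
- **Stopping on Day -1 is not compliant.** Inclusion 9 alone would allow it, but Sections 3.1 and 6.1.1 do not, so that subject deviates from the protocol. The discrepancy needs reconciling; the concern itself rests on a Day -2 stop.
- **Parent roluperidone.** A reader might extend the argument to the roluperidone ratio, on which the sample size is based. The documents link CYP2D6 to BFB-520 and do not say that the parent is cleared by it.
- **The affected pool is narrowed.** Exclusions 1 and 3 remove current major depression, panic disorder, obsessive compulsive disorder and high depression scores. Exclusion 19 names paroxetine, fluoxetine and duloxetine. The urine screen covers tricyclics. This reduces the number at risk, but exclusion 19 concerns required treatment and none of these is a look-back for a stopped inhibitor.
- **The plan leaves room to act.** Protocol 8.2 requires interpretable PK data, SAP 3.3 has a pre-analysis meeting and SAP 5.2.5 permits other PK analyses. These allow a check without committing to one.
- **Depots.** Enrolment at a normal maintenance trough is one reading of the full-cycle wording; the text does not settle it.
- **Residual olanzapine.** Only hypersensitivity to olanzapine excludes, so prior use is possible, and a reader might conclude that leftover olanzapine spoils the reference. Attachment 1 does not list it as a CYP2D6 inhibitor. With an assumed half-life of 21-54 hours, 0.2-9% remains on Day 7. It bears mainly on the Day 1 single-dose profile (21-54% left after 48 hours), which is not in the steady-state ratio.

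**Conclusion.** The point holds for a limited group: subjects who recently stopped a slowly eliminated psychotropic that Attachment 1 lists as a CYP2D6 inhibitor, or a depot antipsychotic. They can be eligible, they stay in both SAP PK sets, and the planned model cannot separate fading inhibition from an olanzapine effect. For BFB-520 the ratio would be too low, provided CYP2D6 clears it as Protocol 1.2 implies.

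The size rests on assumed half-life, inhibition strength and CYP2D6 share: about 1-3% per affected subject at a 1-day half-life and roughly 3-40% at 2-21 days. The effect on the geometric mean also depends on how many subjects are affected. It is zero if none enrol, and the planned summaries would not show which case applies. PK is the secondary objective in the SAP, so this is a cheap improvement and not a flaw that invalidates the study.

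**What to change.** 1. **SAP 5.2.4, before database lock.** Add a drug-by-drug list, based on elimination, of Attachment 1 CYP2D6 inhibitors and depot antipsychotics that could still be present on Day 7. Flag subjects against it using recorded prior-medication stop dates. Protocol 5.8 already has all medications taken before the study entered in the CRF, and the SAP split into prior and concomitant medications needs the stop date. Report the BFB-520 and roluperidone Day 17/Day 7 ratios with and without flagged subjects as a pre-specified sensitivity analysis. Keep the planned set as main, since the reduced set is less precise (working, step 6).
2. **Look for drift.** Inspect the pre-dose and 6-hour concentrations on Days 3-7 and 9-17 in flagged and unflagged subjects. This is supportive only, because accumulation and olanzapine also move these values.
3. **Reconcile the protocol.** Align inclusion 9 with Sections 3.1 and 6.1.1, and state when the depot cycle starts. The sponsor sets the interval.
4. **Optional.** Assay olanzapine in the existing Day 1 pre-dose and Day 7 24-hour samples. This mainly informs the Day 1 profile.

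The cost is SAP wording, the drug list, one extra run and a wider interval in the reduced set. Item 4 adds two assays per subject at draws already planned.
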